10.5.2 Analysis of Key Study Endpoints

10.5.2.1 Efficacy Endpoints

The primary analysis of the primary endpoint will be conducted using the full analysis set. The evaluation period will begin from the date of randomization and subjects will be censored at the last dose of investigational product plus 3 months or end of study, whichever is earlier (on-treatment approach). For the primary endpoint, the proportion of subjects in each treatment group receiving at least 1 RBC transfusion during the evaluation period will be presented with 2-sided 95% CIs. The difference in proportions between treatment groups and the relative risk ratio will be described with 2-sided 95% CIs. Confidence intervals will be derived using normal approximation.

The primary analysis will be repeated by subgroups of stratification factors used at randomization, and also by subgroups of age, gender, race, baseline Hb concentrations and baseline eGFR.

Sensitivity analyses of the primary endpoint will be repeated using all randomized subjects with the evaluation period beginning at the date of randomization and subjects will be censored at the end of study (on-study approach).

Sensitivity analyses will be performed to assess the impact of potential differential follow up on the primary endpoint. Exposure-adjusted subject incidence of receiving at least 1 RBC transfusion will be calculated with 95% CI using Chi-square approximation to the Poisson distribution for both on-treatment and on-study approaches. Other sensitivity analyses, such as completer analyses for investigational product and study, may be performed as appropriate.

The reason for investigational product discontinuation will be reviewed to evaluate its relationship and potential impact on the primary endpoint. Additional transfusion related information collected will be summarized descriptively by treatment group using both on treatment approach and on study approach. These include the transfusion setting and clinical context surrounding transfusions. These summaries will be of transfusion event incidence instead of subject incidence.

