3.2 Sample Size

The objective of the study is to provide estimations with acceptable precision. Thus, the sample size is chosen to ensure that the width of the 95% confidence interval (CI) for the proportion of subjects who receive at least 1 RBC transfusion in each treatment group will be \leq 10% (ie, \pm 5% around the point estimate), assuming the proportion to be 25%. The choice of the precision of the estimated transfusion rate is based on clinical relevance and experience. The estimated proportion of 25% of subjects receiving at least 1 RBC transfusion is based on post hoc analyses in both treatment groups of Trial to Reduce Cardiovascular Events with Aranesp[®] Therapy (TREAT) of subjects who met the eligibility criteria for this study (Amgen data on file) and transfusion rates observed in other studies ([Provenzano et al, 2004](#), [Lawler et al, 2010](#)). To ensure the 95% CI with a width of \leq 10%, 300 subjects per group will be needed to enroll into the study. In order to ensure this precision can be maintained for sensitivity analyses, 20% drop out is accounted for, and enrollment of 375 subjects per treatment group is planned. This total sample size of 750 subjects will also ensure that the width of the 95% CI of the difference in transfusion incidence rates will be \leq 14% (ie, \pm 7% around the point estimate), assuming the proportion of subjects receiving at least 1 RBC transfusion during the study in both treatment groups is 25%. All confidence intervals are derived using normal approximation.

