9.6 Distributional Characteristics

Statistical assumptions for the primary endpoint method of analysis will be assessed. If the assumptions for the primary analysis are not met, then nonparametric methods will be utilized. The use of alternative methods will be fully justified in the CSR.

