10. STATISTICAL METHODS OF ANALYSIS

10.1 General Principles

Descriptive statistics will be presented for all endpoints by treatment group. For continuous variables, these include number of observations, mean, standard error (SE) and/or standard deviation (SD), median, 25th percentile (Q1), 75th percentile (Q3), minimum and maximum. For categorical variables, the frequency and percentage are presented. For time to event endpoints: Kaplan-Meier curves, Kaplan-Meier percentiles, the number of subjects censored, and the number of subjects with events will be summarized. Confidence intervals will be constructed as 2-sided at the 95% level. Summaries of laboratory data, Hb and dose related parameters, and vital signs will be completed using the full analysis set, limited to measurements obtained while the subject is receiving the investigational product.

For variables that are summarized over time, the actual visit for a subject may not exactly coincide with their targeted scheduling. The visit windows defined in [Appendix A](#) will be used to assign evaluations to a most appropriate nominal visit for analysis and summarization.

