10.5.1 Analyses of Primary Efficacy Endpoint(s)

The primary analysis of the primary endpoint will be conducted using the full analysis set. The evaluation period will begin from the date of randomization, and subjects will be censored at the last dose of investigational product plus 3 months or end of study, whichever is earlier (on-treatment approach). For the primary endpoint, the proportion of subjects in each treatment group receiving at least 1 RBC transfusion during the evaluation period will be presented with 2-sided 95% CIs. The difference in proportions between treatment groups will be described with 2-sided 95% CIs. Confidence intervals

will be derived using normal approximation. The relative risk ratio and its 95% CI will be described using the Cochran-Mantel-Haenszel statistic controlling for the stratification factors.

The primary analysis will be repeated by subgroups of stratification factors used at randomization, and also by subgroups of age, gender, race, baseline Hb concentrations, baseline eGFR and diabetes at baseline.

Sensitivity analyses of the primary endpoint will be repeated using:

- All randomized subjects with the evaluation period beginning at the date of randomization and subjects will be censored at the end of study date (on-study approach).
- Completer analysis set with the evaluation period between the date of randomization and the end of study date

Sensitivity analyses will be performed to assess the impact of potential differential follow up on the primary endpoint. Exposure-adjusted subject incidence of receiving at least 1 RBC transfusion will be calculated with 95% CI using Chi-square approximation to the Poisson distribution for both on-treatment and on-study approaches.

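### The plan's normal-approximation intervals have no small-sample provision, so the interval for one group's transfusion proportion may cover only about 80–90% in small subgroup levels

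*SAP*

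**What the plan says.** SAP 10.5.1 says that the intervals for the two group proportions and for their difference "will be derived using normal approximation". Protocol 10.5.2.1 has the same rule: "Confidence intervals will be derived using normal approximation". The level is set in SAP 10.1: "Confidence intervals will be constructed as 2-sided at the 95% level". The relative risk is handled separately in the SAP, with a Cochran-Mantel-Haenszel statistic, and is not at issue here.

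SAP 10.5.1 continues: "The primary analysis will be repeated by subgroups of stratification factors used at randomization, and also by subgroups of age, gender, race", then baseline Hb, baseline eGFR and diabetes. With the definitions in SAP 6.2 that is eight factors and 19 levels: prior transfusion 2, site setting 2, age 3, gender 2, race 3, Hb 3, eGFR 2, diabetes 2. SAP 10.5 allows further subgroups if other prognostic factors emerge.

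The only provision for a failing approximation is in SAP 9.6. Assumptions of the primary method are assessed and, if they are not met, "then nonparametric methods will be utilized", with the alternative justified in the study report. No interval, trigger or subgroup rule is named.

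**The concern.** The trial tests no hypothesis, so its intervals are its results. The normal approximation suits the full groups, but the same formula is carried into each subgroup level whatever its size. Two levels might be small: race Other and the less common site practice setting.

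A Wald interval for a proportion is centred on the observed rate and takes its width from that rate. With few events it is both misplaced and, at low rates, too short. At zero events it collapses to a point, and with one to three events in 20 its lower limit is negative. A reader of the subgroup table would take such an interval as a 95% statement when it is not one.

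**Working it through.** **Inputs.** From SAP 3.2: planned rate 25%, target widths of at most 10% (one proportion) and 14% (difference), 300 per group, 20% dropout, 375 per group. From SAP 10.1: 95%, two-sided, z = 1.96. Subgroup sizes and subgroup rates are not in the documents. I assume 10 to 190 per arm and rates of 5% to 40%.

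**The plan's own figures, by the Wald formula.**
- One proportion: n = z²p(1−p)/0.05² = 3.8415 × 0.1875/0.0025 = 288.1, so 289.
- Difference: n = 2z²p(1−p)/0.07² = 2 × 3.8415 × 0.1875/0.0049 = 293.99, so 294.
- The stated 300 is this rounded up. At 300 the widths are 2z√(0.1875/300) = 9.80% and 2z√(2 × 0.1875/300) = 13.86%.
- 300/0.80 = 375.

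The figures reproduce. The symmetric margins also support reading the method as Wald; SAP 3.2 itself says "All confidence intervals are derived using normal approximation".

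**Intervals compared**, with p̂ = x/n.
- Wald: p̂ ± z√(p̂(1−p̂)/n).
- Wilson: [p̂ + z²/2n ± z√(p̂(1−p̂)/n + z²/4n²)] / (1 + z²/n).
- Newcombe difference: built from the two Wilson intervals (l, u), with limits d − √((p̂₁−l₁)² + (u₂−p̂₂)²) and d + √((u₁−p̂₁)² + (p̂₂−l₂)²).

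Exact coverage is the sum of the binomial probabilities of those x whose interval contains the true p.

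**One case by hand: n = 20, p = 25%.** The Wald interval contains 25% for x = 3 to 9: 0.1339 + 0.1897 + 0.2023 + 0.1686 + 0.1124 + 0.0609 + 0.0271 = 0.895. The Wilson interval contains it for x = 2 to 8: 0.0669 + 0.1339 + 0.1897 + 0.2023 + 0.1686 + 0.1124 + 0.0609 = 0.935. The Wald misses are lopsided: 9.1% come from x ≤ 2.

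**Single-proportion coverage, Wald / Wilson (%).**

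| n per arm | p = 10% | p = 15% | p = 25% |
|---|---|---|---|
| 15 | 79.2 / 94.4 | 89.6 / 93.8 | 90.3 / 96.9 |
| 20 | 87.6 / 95.7 | 81.9 / 97.8 | 89.5 / 93.5 |
| 25 | 91.9 / 96.7 | 89.9 / 95.7 | 89.3 / 93.8 |
| 30 | 80.9 / 97.4 | 94.2 / 96.5 | 94.1 / 96.8 |
| 40 | 91.4 / 94.3 | 93.9 / 95.8 | 94.5 / 95.8 |
| 125 | 92.7 / 96.5 | 92.9 / 95.5 | 94.9 / 95.1 |
| 375 | 94.7 / 94.2 | 94.3 / 94.9 | 94.9 / 95.1 |

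**Where Wald falls below 90%.** Coverage is not monotone in n. The largest n with coverage below 90% is 25 at a 25% rate, 39 at 20%, 52 at 15%, 80 at 10% and 160 at 5%. At 25%, from n = 10 up, only n = 12, 13, 14, 19, 20 and 25 fall below, with a minimum of 82.7% at n = 12. Over rates of 15–40%, the Wald minimum is 81.9% at n = 20, 86.5% at n = 30, 90.5% at n = 50 and 92.9% at n = 125. The Wilson minimum is 92.7% at n = 20 and 92.9% at n = 30.

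**Zero events.** With 0/20, Wald gives 0% to 0% and Wilson 0% to 16.1%. The chance is 0.75²⁰ = 0.3% at a 25% rate and 0.9²⁰ = 12.2% at 10%.

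**Between-arm difference.** With both rates in 15–40%, the Wald minimum is 90.1% at 10 per arm, 92.4% at 20, 93.7% at 30 and 94.7% at 125. Newcombe's minimum is 93.7%, 94.4% and 94.2% at 10, 20 and 30. Outside that range Wald gives 87.5% (10 per arm, 10% vs 20%) and 85.8% (20 per arm, 5% vs 10%; Newcombe 98.6%).

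**Mean widths, Wald vs score.** At a 25% rate: one proportion 8.7% vs 8.7% (n = 375), 9.8% vs 9.7% (n = 300), 36.6% vs 34.7% (n = 20); difference at 375 per arm 12.4% vs 12.4%. At low rates: one proportion, n = 20, p = 10%, 23.4% vs 26.3%; difference, 20 per arm, 5% vs 10%, 30.1% vs 39.9%.

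**The case against.** Most of the plan is untouched. Two- and three-level factors that split evenly hold about 190 or 125 per arm (375/2, 375/3), where single-proportion coverage at rates of 15–40% is about 93% or better. Perhaps one or two levels are small, and nothing in the documents says so. The lowest figures need rates of 10–15%, below the planning value. This stands, and it limits the point to small levels. Rates below 25% are still possible: 25% is an overall planning value, and the on-treatment window closes three months after the last dose.

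A reader might infer that short subgroup intervals will suggest heterogeneity that is not there. The calculations do not support that. Heterogeneity is judged on the difference. At 20 per arm with both rates 25%, the Wald difference covers 93.2% and is wider than Newcombe (52.1% vs 50.8%), so it excludes zero falsely in 6.8% of cases. With both rates 10% the figure is 4.0%.

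A reader might also extend the point to the adverse-event risk differences in SAP 10.6.1. That section names no interval method, and the sentence in SAP 3.2 belongs to the sample-size calculation, so no defect is shown there.

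The documents never say Wald, and a Wilson interval also rests on a normal approximation. The SAP's code fragments (Appendix B) are blacked out and might name an option. SAP 9.6 shows that a failing approximation was foreseen. These are fair reservations, but the readable text leaves the interval unspecified, and the word nonparametric does not identify one for a proportion.

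**Conclusion.** The point holds in a limited form. If the normal approximation means Wald, the interval for a single group's transfusion proportion can cover about 80–90% in small subgroup levels: at about 25 or fewer per arm if the true rate is 25%, and up to about 40–80 per arm if it is 10–20%. With very few subjects and a low rate it dips slightly further (79.2% at n = 15, p = 10%). With zero events the interval has no width.

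Subgroup sizes and rates are assumptions. The overall primary interval, levels of 125 or more per arm at rates of 15% or higher, and between-arm differences at rates of 15–40% are little affected. Severity is low: the subgroup results are descriptive and the main result does not change.

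**What to change.** In SAP 10.5.1, state that group proportions have Wilson intervals and differences have Newcombe or Miettinen-Nurminen intervals, in the overall analysis and in all subgroups. Use the same sentence to replace the open-ended fallback in SAP 9.6 for this endpoint. Because Protocol 10.5.2.1 also specifies the normal approximation, record the choice in SAP Section 11, which now reports no changes.

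The cost is one or two sentences and a software option. Planned N and target precision are unchanged. The downside is at low event rates, where the score intervals are wider and Newcombe is conservative: at 20 per arm with 5% vs 10%, mean width is 39.9% instead of 30.1%, with coverage of 98.6% instead of 85.8%.

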10.5.2 Analyses of Secondary Efficacy Endpoint(s)

Total number of units of RBC transfused per subject will be described for each treatment group, and will be analyzed using a negative binomial regression model which will

include the stratification factors used at randomization. As a sensitivity analysis, exposure adjusted event incidence of total number of units RBC transfused will be presented with 95% CI using Chi-square approximation to the Poisson distribution. These analyses will be performed using both on-treatment approach with the full analysis set and on-study approach with all randomized subjects.

Time to first RBC transfusion will be analyzed using both on-treatment approach with the full analysis set and on-study approach with all randomized subjects. It will be analyzed by each treatment group with Kaplan-Meier curves, Kaplan-Meier percentiles and estimates at 6, 12, 18, and 24 months, the number of subjects censored, and the number of subjects transfused. A supportive analysis will be performed using Cox proportional hazards model (Cox, 1972) stratified by the stratification factors used at randomization to evaluate the difference between the treatment groups. The hazard ratio and its corresponding 95% CI will be estimated.

Average achieved Hb concentration while receiving investigational product will be described as average Hb using the area under the curve (AUC) method. The median of the difference in achieved Hb concentration (Hodges–Lehmann estimate) between treatment groups will be calculated and 2-sided 95% confidence limits will be derived by using a nonparametric Wilcoxon rank-sum statistic (Hollander and Wolfe, 1973). As a sensitivity analysis, the above analyses will be repeated excluding Hb concentrations measured within 3 months (84 days) from an RBC transfusion.

Cumulative doses of darbepoetin alfa adjusted for investigation product exposure time (eg, average cumulative darbepoetin alfa dose per 4 week) will also be summarized, and the median of the difference (Hodges–Lehmann estimate) between treatment groups will be calculated and 2-sided 95% confidence limits will be derived by using a nonparametric Wilcoxon rank-sum statistic.

The descriptive summary of total number of RBC transfused, time to first RBC transfusion, average achieved Hb concentration while receiving IP and cumulative doses of darbepoetin alfa adjusted for IP exposure time by randomized treatment group, using the on-treatment approach, will be repeated by subgroups of stratification factors used at randomization, and also by subgroups of age, gender, race, baseline Hb concentrations baseline eGFR and diabetes at baseline.

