Subjects randomized to the fixed dose group will receive a fixed dose of darbepoetin alfa throughout the study of 0.45 µg/kg, based on the subject's screening weight, rounded down to the next lower PFS strength. The same dose of darbepoetin alfa will then be administered Q4W for the duration of the study, with 1 exception: if the Hb is > 12.0 g/dL, the darbepoetin alfa dose will be withheld and placebo will be administered until the Hb falls below 10.0 g/dL, at which time the darbepoetin alfa dose will be restarted. In order to maintain the blind when a subject in the Hb-based titration group is assigned 2 injections of investigational product, subjects in the fixed dose group will be assigned at random to receive 2 injections of investigational product.

Throughout the study, investigators should provide adequate supportive care. It is recommended that iron be administered to ensure TSAT levels of ≥ 20% and serum ferritin ≥ 100 ng/mL and blood pressure be monitored and managed as appropriate, such as to target a SBP < 130 mmHg and a diastolic blood pressure (DBP) < 80 mmHg. Subjects should not receive any other ESAs while receiving investigational product during the study.

Procedures

Informed consent will be obtained prior to the execution of any study procedures. Subject visits and assessments will occur from the time of screening through the end of study. At the conclusion of the screening period, eligible subjects will be randomized in a 1:1 ratio to 1 of 2 dosing strategies:

- Hb-based titration group: Darbepoetin alfa titrated to maintain Hb ≥ 10.0 g/dL
- Fixed dose group: Weight-based dose of darbepoetin alfa that will not be titrated

Randomization will be stratified by RBC transfusion received within 12 months prior to randomization (yes/no) and site practice setting (nephrology/non-nephrology).

Assessments during the study visits may include:

- Recording of transfusions, adverse events, concomitant medications, hospitalizations and collection of study endpoint data for adjudication
- Physical assessments (eg, blood pressure)
- Collection of laboratory samples for evaluation of blood chemistry, hematology and iron status
- Collection of blood samples for biomarkers

Subjects ending investigational product prior to week 97 will be asked to complete scheduled visits and study procedures. At a minimum, subjects must be followed for the collection of RBC transfusions and endpoint data for adjudication.

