10.5.2.2 Secondary Endpoints

Total number of units of RBC transfused per subject will be described for each treatment group, and will be analyzed using a negative binomial regression model which will include the stratification factors used at randomization. As a sensitivity analysis, exposure adjusted event incidence of total number of units RBC transfused will be presented with 95% CI using Chi-square approximation to the Poisson distribution. These analyses will be performed using both on-treatment and on-study approaches.

Time to first RBC transfusion using both on-treatment and on-study approaches will be analyzed by each treatment group with Kaplan-Meier curves, Kaplan-Meier percentiles, the number of subjects censored, and the number of subjects transfused. A supportive analysis will be performed using Cox proportional hazards model ([Cox, 1972](#)) stratified by the stratification factors used at randomization to evaluate the difference between the treatment groups. The hazard ratio and its corresponding 95% CI will be estimated.

Average achieved Hb concentration while receiving investigational product will be described as average Hb using the area under the curve (AUC) method. The median of the difference in achieved Hb concentration (Hodges–Lehmann estimate) between treatment groups will be calculated and 2-sided 95% confidence limits will be derived by using a nonparametric Wilcoxon rank-sum statistic ([Holander and Wolfe, 1973](#)).

Cumulative doses of darbepoetin alfa adjusted for investigation product exposure time will also be summarized, and the median of the difference (Hodges–Lehmann estimate) between treatment groups will be calculated and 2-sided 95% confidence limits will be derived by using a nonparametric Wilcoxon rank-sum statistic.

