For time to event such as time to first transfusion, or time to first major clinical event (eg, major adverse cardiovascular events (MACE), all-cause mortality), time to event is derived from the randomization date to the date of specific event. Subjects that do not experience the event will be censored. For time to event analysis using the on-treatment approach, the censoring date is the last dose date + 3 months (84 days) or the end of study date, whichever is earlier. For time to event analysis using the on-study approach, the censoring date is the end of study date.

Context surrounding RBC Transfusion

Clinical context surrounding RBC transfusion will be collected for each RBC transfusion event, and will be reviewed by an independent Clinical Endpoint Committee (CEC). The clinical context includes the primary reason for the transfusion event, the transfusion setting (eg, dialysis center, intensive care unit, emergency department), Hb at the time of the first transfusion of the transfusion event, clinical events (eg, bleeding, surgery), symptoms and vital signs of concerns.

Total number of units of RBC transfused

The total number of units of RBC transfused using the on-treatment approach is the sum of RBC units transfused between the randomization date and the earlier date of the last dose date + 3 months (84 days) and the end of study date. The total number of units of RBC transfused using the on-study approach is the sum of RBC units transfused between the randomization date and the end of study date.

Number of Days Hospitalized

This is the total number of days of hospitalization between the randomization date and earlier of the date of last IP + 3 months (84 days) and the end of study date for the on-treatment approach; between the randomization date and the end of study date for the on-study approach. Duration of each hospitalization stay is calculated as day of discharge - day of admission + 1. Hospitalizations with identical admission and discharge days will be counted as a hospitalization with duration of 1 day.

Area under the Curve (AUC) Calculation

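### The text for the negative binomial model of RBC units names no follow-up offset; if follow-up differs between arms, the count ratio understates the burden of the arm observed for less time

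*SAP*

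**What the plan says.** Protocol 10.5.2.2 has total units per subject "analyzed using a negative binomial regression model which will include the stratification factors used at randomization". SAP 10.5.2 repeats this: the model will "include the stratification factors used at randomization. As a sensitivity analysis, exposure adjusted event incidence of total number of units RBC transfused" is to be presented with a 95% CI from the chi-square approximation to the Poisson distribution. Neither text names an offset, a log follow-up term or an exposure covariate.

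The outcome is a plain sum. SAP 6.3 defines the on-treatment total as "the sum of RBC units transfused between the randomization date and the earlier date of the last dose date + 3 months (84 days", the other limit being each subject's end of study; the on-study total runs to the end of study date. Both approaches are planned: on-treatment in the full analysis set and on-study in all randomized subjects.

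SAP 10.5.1 raises possible differential follow-up, but for the primary endpoint only. SAP Appendix B (code fragments) is redacted.

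**The concern.** A count model without an offset estimates a ratio of mean counts. When subjects are observed for different lengths of time, that ratio is the rate ratio multiplied by the ratio of time observed. A completer is followed for about 700 days. A subject who stops after one dose contributes about 84 days on-treatment, and less after early death or withdrawal.

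Unequal stopping is possible. Only the titration arm can be dosed upwards (Protocol 6.4.1.2), and lack of efficacy is a listed reason to end product (Protocol 8.1). Transfusion burden is the first secondary objective, and Protocol 2.3 counts total units among the considerations for choosing a preferred regimen. A ratio that partly reflects time observed could mislead that choice.

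**Working it through.** **1. The plan's own figure.** The documents give no figure for the units model. The nearest is the sample size, which fixes the arm size and the 25% transfused used below. SAP 3.2 says "300 subjects per group will be needed to enroll into the study" and "20% drop out is accounted for, and enrollment of 375 subjects per treatment group is planned".
- n for a half-width of 5 points at 25%: 1.96² × 0.25 × 0.75 / 0.05² = 288.1, so 289; the plan uses 300.
- 300 / (1 − 0.20) = 375.
- CI width at 300: 2 × 1.96 × √(0.1875/300) = 9.80%. For the difference: 2 × 1.96 × √(2 × 0.1875/300) = 13.86% (12.40% at 375).

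The stated precision is reproduced.

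**2. Mean on-treatment window.** From the documents: 100 weeks on study (Protocol 3.4.1), so 700 days; dosing visits to week 97, which is 672 days after randomization; window = min(last dose + 84, 700). Assumed, not in the documents: early stoppers' last dose is uniform over 0 to 672 days, and nobody leaves the study early.
- Last dose by day 616 (616/672 = 0.917 of stoppers): mean window 308 + 84 = 392 days.
- Last dose later (0.083): 700 days.
- Stoppers overall: 0.917 × 392 + 0.083 × 700 = 417.7 days.
- Whole arm with fraction d stopping: 700 − 282.3d, that is 672, 644, 615, 587, 559 and 531 days at 10%, 20%, 30%, 40%, 50% and 60%.

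**3. Expected ratio without an offset.** With the same unit rate in both arms, unrelated to stopping, expected units are rate × mean window. The expected count ratio is therefore the ratio of mean windows.

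| Stopping, arm A vs B | Mean windows (days) | B/A count ratio, true ratio 1 |
|---|---|---|
| 20% vs 20% | 644, 644 | 1.000 |
| 10% vs 20% | 672, 644 | 0.958 |
| 20% vs 30% | 644, 615 | 0.956 |
| 20% vs 40% | 644, 587 | 0.912 |
| 20% vs 50% | 644, 559 | 0.868 |
| 30% vs 60% | 615, 531 | 0.862 |

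This is the 4% to 14% range. If stops cluster early, the effect is larger: 30% vs 50% with mean windows of 81 and 68 weeks gives 68/81 = 0.84.

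**4. Simulation of the fitted models.** 250 trials per row, 375 per arm, gamma-Poisson units with dispersion set so that 25% are transfused over full follow-up; negative binomial regression on arm and two strata. Ratios are medians of B/A.

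| Mean units | Stopping | True ratio | No offset | Log-window offset | CI excludes 1: none / offset |
|---|---|---|---|---|---|
| 0.5 | 20% vs 40% | 1.0 | 0.907 | 0.999 | 8.0% / 5.2% |
| 1 | 20% vs 40% | 1.0 | 0.923 | 1.016 | 8.8% / 6.8% |
| 2 | 20% vs 40% | 1.0 | 0.894 | 0.988 | 10.8% / 6.0% |
| 1 | 20% vs 20% | 1.0 | 0.984 | 0.995 | 6.4% / 6.4% |
| 1 | 20% vs 50% | 1.0 | 0.871 | 1.006 | 11.2% / 7.2% |
| 1 | 20% vs 40% | 1.3 | 1.203 | 1.300 | 15.6% / 26.4% |

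Monte Carlo error on the percentages near 5% to 11% is about 1.5 to 2 points.

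**5. The planned Poisson interval.** In these settings the variance-to-mean ratio of units is 2.8, 8.4 and 22.7 at means of 0.5, 1 and 2; Poisson assumes 1. The interval is then too narrow by a factor of about √2.8 = 1.7 to √22.7 = 4.8. A Poisson-based rate-ratio interval excluded 1 in 25%, 53% and 70% of the equal-rate trials at 20% vs 40% stopping.

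**6. Bias against precision.** The standard error of the log ratio is about 0.22 at a mean of 1 unit, so the 95% CI extends by a factor of exp(1.96 × 0.22) = 1.54 each way. The bias is ln 0.956 = −0.045 (0.2 SE) at 20% vs 30% stopping and ln 0.868 = −0.142 (0.6 SE) at 20% vs 50%.

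**The case against.** **The sentence may not be the whole model.** It says what the model includes, not that nothing else enters. It does not even name the treatment term, and an offset is usually set in code, which is redacted here. This stands: a reader might infer that the offset is certainly absent, and the documents cannot show that. The text still points that way. Exposure adjustment comes next as a sensitivity analysis, the planned tables (SAP 12.1) list the two analyses separately, and the same section says so explicitly when cumulative dose is adjusted for exposure.

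**Differential stopping is not documented.** No stopping rate by arm is given; the only figure is 20% drop-out overall. The fixed dose was chosen to reach about the same mean Hb (Protocol 2.3), and investigators are blinded. This stands, and the size is therefore conditional. The documents do not support an inference that one named arm will stop more.

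**Much is covered elsewhere.** Exposure-adjusted incidence of units is planned for both approaches, time to first transfusion is analysed with censoring, and SAP 10.5.1 adds a composite of transfusion or stopping for lack of efficacy. This stands in part. The rate-scale point estimates help, but the Poisson interval does not handle clustering and no between-arm ratio is promised. The denominator is also open: SAP 6.3 defines exposure to product with 28 days after the last dose, while the count uses 84.

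**The analysis is descriptive and the bias small against the interval.** True in moderate scenarios, as step 6 shows. It bears on priority, not on whether the model should be stated correctly.

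**Conclusion.** The point holds in conditional form. As the text reads, the main model compares counts over unequal windows. If one arm is followed for less time, its burden is understated, by about 4% to 14% for 10- to 30-point differences in evenly spread stopping, and by more if stops come early. With equal follow-up there is no such bias. The stopping patterns, unit means and dispersions are assumptions.

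A reader might infer that the arm that stops earlier will look as if it has the lower burden. That follows only when true rates are about equal: with a true ratio of 1.3 against that arm, the model without an offset still showed 1.20, so the excess shrank but did not reverse. Nor does the point apply equally to both approaches. Stopping product does not itself end the on-study window, since Protocol 7.1.5 and 8.1 keep subjects in follow-up for transfusions; only death, withdrawal or loss shortens it.

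An offset is not a complete cure. When stopping was made to depend on transfusion risk in two further simulated settings, ratios were 0.81 and 0.73 without an offset and 0.96 and 0.95 with one.

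**What to change.** Confirm whether the redacted code already contains an offset. Either way, add to SAP 10.5.2:

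*The log of each subject's evaluation period will be the offset in the negative binomial model, using the same window as the count: on-treatment, randomization to the earlier of last dose + 84 days and end of study; on-study, randomization to end of study. The rate ratio between treatment groups and its 95% CI will be reported for both approaches side by side.*

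Name the same windows as denominators for the exposure-adjusted incidence of units, and count the randomization day so that no window has length zero.

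The cost is a sentence or two in the SAP and one model option. No new data are needed, and the endpoint and sample size do not change.
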